4.2.2.7 Subgroup Analyses

Not applicable

4.2.3 Secondary Endpoints for RTP phase

4.2.3.1 Definition

The secondary efficacy endpoints for RTP phase will include the following:

- 1. The proportion of subjects who remain normokalemic (as defined by S-K levels between 3.5-5.0 mmol/L, inclusive) at the end of the RTP and during the RTP (Day 8 to Day 29).
- 2. The number of days subjects remain normokalemic during the RTP (Day 8 to Day 29).
- 3. The time to the first instance of hyperkalemia (defined as S-K \geq 5.1 mmol/L).
- 4. The mean changes in S-Aldo and P-Renin levels.

4.2.3.2 Derivations

See section 3.3.1.1 for definition of baseline for the efficacy endpoints.

The number of days subjects remain normokalemic is calculated as the sum of the length of each period of normokalemia a subject has. The length of a period of normokalemia is calculated as the stop date of normokalemia – start date of normokalemia + 1. For subjects who have a period of normokalemia lasting for a single visit, the duration of this period is set to 1. For subjects who have a time point missing in between two visits where the subject was recorded as being normokalemic, it can be assumed that the subject remained normokalemic and extend the period of normokalemic during the RTP, the number of days subjects remain normokalemic is set to 0.Time to hyperkalemia is defined as the number of days from randomization to the date of hyperkalemia = (date of hyperkalemia -date of randomization) +1.

For analysis of time to hyperkalemia, subjects who discontinue treatment in RTP due to high S-K levels (i-STAT potassium levels > 6.2 mmol/l at the 90-minute post dose 2 blood draw) will be treated the same as the subjects who developed hyperkalemia (event). Subjects who do not become hyperkalemic during RTP will be censored at the time of the last S-K measure available for the RTP.

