3.3.7 Multiplicity/Multiple Comparisons

A sequential closed testing procedure will be used in OLP and RTP to maintain an overall Type I error rate of 5%.

Treatment testing will proceed from high dose (ZS 10g) to low dose (ZS 5g) relative to placebo, with statistical significance (two-sided p-value ≤ 0.05) required for the high dose vs. placebo control in order to proceed to the low dose vs. placebo control.

P-values for tests not included in the sequential closed testing procedure are not adjusted for multiplicity and will not be called significant and are considered exploratory.

Specifically, the following fixed hierarchical sequence will be employed: progression to the next test in the sequence will continue until a 2-sided p-value of > 0.05 is encountered, at which any point further testing will cease. Explicitly, Table 3 will be implemented.

D9480C00001 - ed. 3.0

Table 3. Overview of the variables/endpoints and multiplicity testing order

	Endpoints/Variables	Phase	Treatment Comparison	Testing Order in Hierarchy
N	Mean serum potassium [S-K] level		ZS 10g QD vs. Placebo	2
naı	Mean serum potassium [S-K] level		ZS 5g QD vs. Placebo	3
Prin				
	Proportion of subjects who remain normokalemic ^{iv} at the end of RTP ⁱⁱⁱ		ZS 10g QD vs. Placebo	4
	Proportion of subjects who remain normokalemic at the end of RTP	RT	ZS 5g QD vs. Placebo	5
y.	Number of days that subjects are normokalemic		ZS 10g QD vs. Placebo	6
dar	Number of days that subjects are normokalemic		ZS 5g QD vs. Placebo	7
OU	Time to hyperkalemia ^v		ZS 10g QD vs. Placebo	8
Sec	Time to hyperkalemia		ZS 5g QD vs. Placebo	9
	Mean serum potassium [S-K] change from baseline after first dose	OLP	NA	1

ⁱ OLP refers to the 24 or 48 hours Open Label Phase.
 ⁱⁱ RTP refers to the 28 days Randomized Treatment Phase, and Days 8-29 is of interest for the endpoints.
 ⁱⁱⁱ End of RTP in the maintenance day refers to the planned day of last dose of study treatment, Day 29.
 ^{iv} Normokalemic/Normokalemia is defined as having [S-K] level within the range of 3.5-5.0 mmol/L, inclusive.

^v Hyperkalemia is defined as having [S-K] level greater equal than 5.1 mmol/L.

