4.2.3.3 Primary Analysis of Secondary Endpoints for RTP

Descriptive statistics will be presented for S-K levels for all timepoints for each S-K was scheduled to be measured, as well as OLP baseline. The statistics will include the mean change (absolute and percent change) from baseline. In addition, a plot of S-K values by timepoint will be presented.

Similarly, the proportion of subjects who remain normokalemic will be presented by study visit.

Proportion of subjects normokalemic at Study Day 29

For the Day 29, the likelihood of being normokalemic will be compared using a logistic regression model containing the same baseline covariates as for the primary efficacy endpoint with the exception of visit and the visit-by-treatment interaction (see Section 4.2.1.4). The estimated odds ratios corresponding to the difference between the treatment arms, 95% 2-sided CI and p-values will be provided.

Proportion of subjects normokalemic during the RTP

The likelihood of being normokalemic during RTP will be analyzed using a generalized mixed model (SAS PROC GLIMMIX), which includes a random intercept and logit link. The model will include all S-K data values collected at the scheduled visits between Days 8-29, dichotomized as normal and abnormal, as response variables, and the same covariates as the model used for the main analysis of the primary endpoint (See Section 4.2.1.4).Similarly, to the approach used for the primary analysis, the model will attempt to incorporate different (unstructured) degree of dependence between the repeated observations and, if issues with model fit are observed, switch to simplified dependence structures (see Section 3.3.6). The estimated odds ratios corresponding to the difference between the treatment arms, 95% 2-sided CI and p-values will be provided.

Number of days subjects remain normokalemic

The number of normokalemic days during the RTP, inclusive of Days 8-29, will be calculated assuming that the time interval between assessments is normokalemic only if both the beginning and end assessments for that time interval display normal S-K values.

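### Do SAP 4.2.3.2 and 4.2.3.3 give two conflicting counts of normokalemic days for confirmatory tests 6 and 7?

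*SAP*

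**What the plan says.** - **Role of the endpoint.** SAP 3.3.7, Table 3, lists "Number of days that subjects are normokalemic" as test 6 (10 g vs placebo) and test 7 (5 g vs placebo). Because "progression to the next test in the sequence will continue until a 2-sided p-value of > 0.05 is encountered", these two tests gate tests 8 and 9 (time to hyperkalemia).
- **SAP 4.2.3.2 (Derivations).** The score is the sum over a patient's normokalemic periods. "The length of a period of normokalemia is calculated as the stop date of normokalemia – start date of normokalemia + 1". An isolated normal visit has its own rule: "For subjects who have a period of normokalemia lasting for a single visit, the duration of this period is set to 1". A missing visit between two normal ones is bridged. A patient with no normokalemia appears to score 0, although that sentence is run together in the text as read.
- **SAP 4.2.3.3 (analysis).** "The number of normokalemic days during the RTP, inclusive of Days 8-29" is the quantity to be calculated, on the assumption that a "time interval between assessments is normokalemic only if both the beginning and end assessments for that time interval display normal S-K values".
- **SAP 4.2.3.6.** The bridging of a missing intermediate visit is repeated.
- **SAP amendment history.** The 4.2.3.2 derivation was added on 12 August 2022, and the stated reason is clarification of the logic.

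**The concern.** One confirmatory endpoint is described in two sections, in different terms, and neither refers to the other on this point. Section 4.2.3.2 adds a day to every period and credits a lone normal visit. Section 4.2.3.3 speaks only of intervals with two normal ends, and a lone normal visit has no such interval on either side. A programmer working from 4.2.3.3 alone could add up the qualifying gaps and stop there. That total is lower than the 4.2.3.2 total by one day per separate period.

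If both rules were live, reported means and SDs, and possibly a borderline p-value in a gating test, would depend on which section was programmed. The inclusive rule might also seem to reward a patient who loses and regains control. And since the derivation entered the SAP in August 2022, the choice could look as if it had been made with data in hand.

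**Working it through.** The SAP states no scale maximum, power or sample size for this endpoint, so there is no plan figure to reproduce.

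**Inputs.** Scheduled visits in the window (SAP Table 2): Days 8, 12, 15, 19, 22, 26, 29. Successive gaps: 4, 3, 4, 3, 4, 3. Each visit is normal or abnormal, so there are 2^7 = 128 patterns.

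**Step 1: the apparent conflict.** Compare the 4.2.3.2 formula with a bare sum of gaps that have two normal ends.

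| Normal visits | 4.2.3.2 | Bare gap sum |
|---|---|---|
| All seven | 29 − 8 + 1 = 22 | 4+3+4+3+4+3 = 21 |
| All but Day 15 | (12 − 8 + 1) + (29 − 19 + 1) = 16 | 4 + (3+4+3) = 14 |
| Days 8, 15, 22, 29 | 1+1+1+1 = 4 | 0 |
| Day 29 only | 1 | 0 |

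The difference always equals the number of separate periods: 0 in 1 pattern, 1 in 28, 2 in 70, 3 in 28 and 4 in 1. The 4-versus-0 case is the single most extreme pattern.

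**Step 2: what 4.2.3.3 governs.** Its sentence is about the interval between assessments. It does not say that a visit day with a normal measured value is discarded. It gives neither a maximum of 21 nor a score of 0 for a lone normal visit. Its window includes both Day 8 and Day 29, which is 29 − 8 + 1 = 22 calendar days. A bare gap sum can never reach 22.

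**Step 3: the two sections applied together.** Take each calendar day from 8 to 29. A visit day counts if its own S-K is normal. A day between visits counts only if both adjacent visits are normal (4.2.3.3). For a run of consecutive normal visits from day a to day b:

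- every day from a to b is either a normal visit day or lies between two normal visits, so the run contributes b − a + 1;
- every day outside a run is an abnormal visit day or has at least one abnormal neighbour, so it contributes 0;
- with a = b the contribution is 1.

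That is the 4.2.3.2 formula, including its single-visit rule. Enumeration confirms equality in 128 of 128 patterns. The argument does not depend on exact visit dates, and it covers a bridged missing visit, whose day simply becomes a day between two observed visits.

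**Step 4: the stop date.** Section 4.2.3.2 does not define when a period stops. Taking the first abnormal visit would change 74 of 128 scores; for normal values at Days 8 and 12 only, 15 − 8 + 1 = 8 instead of 12 − 8 + 1 = 5. Section 4.2.3.3 rules this out, because the Day 12-15 interval has an abnormal end. The stop is the last normal visit.

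**Step 5: is loss of control rewarded?** One abnormal visit at Day 15 lowers the 4.2.3.2 score from 22 to 16. The 6 days lost are Days 13 to 18. The bare gap sum falls from 21 to 14, a loss of 7. Losing control costs days either way, and each isolated day credited is one on which a normal value was measured.

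**Step 6: size if the bare gap sum were used anyway.** Assume per-visit probabilities of a normal value of 0.75 (active) and 0.45 (placebo), with 100 and 50 patients.

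| Within-patient persistence | Difference in days, 4.2.3.2 | Difference in days, gap sum | Shift | z, 4.2.3.2 vs gap sum |
|---|---|---|---|---|
| 0 | 7.55 | 7.63 | 0.08 | 9.66 vs 9.29 |
| 0.5 | 7.03 | 6.91 | 0.12 | 6.16 vs 6.08 |
| 0.8 | 6.96 | 6.73 | 0.23 | 4.67 vs 4.66 |

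A second simulation used S-K arm means of 4.5, 4.8 and 5.1, between-patient SD 0.3-0.5 and within-patient SD 0.3-0.4. The between-arm shift was 0.01 to 0.19 day. For scale, protocol 1.3.3 (Figure 2) gives 6.5 days (3.67 to 9.33) for 10 g, an implied SE of (9.33 − 3.67)/(2 × 1.96) = 1.44. The largest shift, 0.23 day, is 0.23/6.5 = 3.5% of that effect and 0.23/1.44 = 0.16 SE.

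**The case for a change.** The best case for the concern is that the joint reading has to be put together by the reader. Section 4.2.3.3 is silent on the visit day itself, both intervals beside a lone normal visit fail its test, and 0 is what a literal programmer might return. A confirmatory derivation should not depend on inference, and the stop date is settled only by bringing in the other section.

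The silence is real, and a cross-reference between the sections would be tidier. But 4.2.3.2 answers the open question expressly: a lone normal visit scores 1. It is the section headed as the derivation, and the amendment history records it as the text added to clarify the logic. Reading 4.2.3.3 as a bare gap sum means overriding that explicit rule and disregarding the inclusive window. It would also give 0 normokalemic days to a patient normal only at Day 29, whom tests 4 and 5 count as normokalemic.

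The timing point does not stand. Protocol 8.1 keeps analysis personnel blinded until database lock and requires the SAP to be final before then. The documents give no lock date, and nothing in them suggests that the August 2022 clarification was made with knowledge of treatment allocation.

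**Conclusion.** The concern does not hold. The two sections do different jobs, one classifying the days between visits and the other counting days, and together they define one score that runs from 0 to 22. The scores of 21 and 0 appear nowhere in the SAP; they come from a reading that goes against its inclusive window and its single-visit rule. Replacing the count with a gap sum would be a preference, not a correction.

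This rests on counting a visit day by its own measured value, the natural sense of an inclusive day count, and on the run-together sentence in 4.2.3.2 being the rule for patients who are never normokalemic. What remains is a missing cross-reference. Were the other reading programmed by mistake, arm means would drop by roughly 1 to 2 days (0.74 to 1.95 in the first simulation, 1.2 to 1.7 in the second). The treatment difference would move by only about 0.2 day at most. Those sizes depend on assumed inputs; the agreement between the sections does not.

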- 18. The defined wider visit window can be applied, if patients are not able to strictly follow the pre-specified visit schedules, due to a prolonged public holiday.

Study Visit	Rand. Visit	Visit 6	Visit 7	Visit 8	Visit 9	Visit 10	Visit 11	Visit 12	Visit 13	Visit 14	EOS 9
28-day randomized treatment study phase Day ⁷	Day 1 ¹²	Day 2 ¹²	Day 5 ¹²	Day 8 ¹²	Day 12 ¹²	Day 15 ¹²	Day 19 ¹²	Day 22 ¹²	Day 26 ¹²	Day 29 ¹²	Day 35 ¹²
Accepted visit window during prolonged public holidays ⁸			Day 3-6	Day 7-9	Day 10-13	Day 14-17	Day 18-20	Day 21-24	Day 25-27	Day 28-31	Day 32-43
Eligibility criteria	Х										
Physical exam including weight ^{3, 13}	Х					Х				Х	Х
Access IVRS/IWRS ¹⁰	Х			Х		Х		Х			
Study drug (IP) dispensation ¹¹	Х			Х		Х		Х			
Study drug (IP) administration ⁴	Х	Х	Х	Х	Х	Х	Х	Х	Х		
ECG ³	Х			Х		Х		Х		Х	Х
Vital signs ³	Х					Х				Х	Х
Concomitant medications	Х	Х	Х	Х	Х	Х	Х	Х	Х	Х	Х
Adverse events (including SAEs)	Х	Х	Х	Х	Х	Х	Х	Х	Х	Х	Х
Potassium ⁶	X^2	Х	Х	Х	Х	X^2	Х	Х	Х	X^2	X^2
Clinical chemistry ^{1,3}	Х					Х				Х	Х
Hematology ^{1,3}	Х					Х				Х	Х
Urinalysis 1,3	Х					Х				Х	Х
Urine HCG											X^5
IP Reconciliation										Х	

Table 2Study Plan detailing the procedures: 28-day randomized treatment study phase

1. Parameters to be measured are detailed in Table 3.

2. Potassium will be measured fasting prior to the 1st daily dose as part of the clinical chemistry panel on Day 1, 15, 29, 35 in the 28-day randomized treatment study phase.

3. Physical Exam, ECG, Vital signs, weight, urinalysis, clinical chemistry including S-Aldo and P-Renin, and hematology parameters will be measured fasting (nothing by mouth except water for a minimum of 8 hours prior to potassium sample collection at the clinic); On the 28-day randomized treatment study phase Days 1,15, 29, and 35(EOS), blood sample which including S-Aldo and P-Renin test need to be collected prior to 10am after the patient has been upright for at least 2 hours and before the ECG.

4. Study drug will be administrated in the clinic on Day 1,2,5,8,12,15,19,22 and 26. If a patient develops i-STAT potassium values between 3.0 mmol/L and 3.4 mmol/L, inclusive (confirmed by taking a second potassium

measurement after a 10 ± 2 -minute interval, and both i-STAT values meet the study drug adjustment rule), dosing will be reduced from qd to every other day for the remainder of the study.

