4.4 Follow-up period (EOS)

Follow up visit will be performed at Day 9 for the open-label initial phase, and Day 35 for the 28-day randomized treatment study phase, or 7 ± 1 days following the last study IP administration for patients who are withdrawn from the study.

[figure not shown]
Patients will arrive at the clinic in the morning, fasting (nothing by mouth except water for a minimum of 8 hours prior to potassium sample collection at the clinic).

[figure not shown]
The following assessments will be performed:

- The clinic staff will solicit any AEs, note any changes in concomitant medications on the eCRF and source documents.
- Vital signs (pulse rate and blood pressure) will be obtained.
- The following tests/procedures will be performed:
 - i-STAT blood potassium assessment
 - Blood samples for a standard assessment of clinical chemistry including, S-K
 - Blood for a standard assessment of hematology parameters
 - Urine for standard urinalysis parameters
 - A pregnancy test if the patient is a woman of childbearing potential
 - An ECG will be performed (Section 5.2.3)
 - A targeted physical examination will be performed (Section 5.2.2)

[figure not shown]
Note: If the EOS for the open-label initial phase or the 28-day randomized treatment study phase falls on a weekend or a short public holiday, the EOS visit can be performed either on the preceding Friday or the following Monday.

If the EOS for the open-label initial phase falls on a prolonged public holidays, the EOS visit can be performed from Study Day 4 to Study Day 16. If the EOS for the 28-day randomized treatment study phase falls on a prolonged public holidays, the EOS visit can be performed from Study Day 32 to Study Day 43. This will only apply during prolonged public holidays.

[figure not shown]

Clinical Study Protocol Drug Substance ZS Study Code **D9480C00001** Version **6.0** Date **19** August 2020

63 (101)

Clinical Study Protocol Drug Substance ZS Study Code **D9480C00001** Version **6.0** Date **19** August 2020

- 1. The open-label initial phase Day 3 is also the same day as the Randomization Visit (Day 1) of the 28-day randomized treatment study phase. Patients achieving normokalemia in the morning of the open-label initial phase Day 2 will enter the Study Day 1 of the 28-day randomized treatment study phase directly.

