3.3.3 Visit Window

In the absence of nominal visits, visits windows will apply. Measurements will be assigned to exhaustive visit windows based on study day such that measurements taken at any time point can be accounted for and used in summaries and/or analyses. If an unscheduled visit occurred in the same window, then the measurement from the scheduled visit will be used in the analysis. If there are multiple unscheduled visits in the same visit window, then the visit closest to the scheduled visit day will be used. If there are multiple records on the same day the last measurement will be used.

- For summaries showing the maximum or minimum values, the maximum/minimum value recorded on treatment is used (regardless of where it falls in an interval).
- Listings display all values contributing to a time point for a subject.
- For visit-based summaries
 - If there is more than one scheduled value per subject within a time window then the closest value to the scheduled visit date is summarized. If the scheduled values are equidistant from the nominal visit date, then the earlier value is used. Data listings will highlight the values used in the summary table, wherever feasible.
 - Note: in summaries of extreme values (i.e. when assessing the minimum/maximum on-treatment values), all post baseline values collected are used including those collected at unscheduled visits regardless of whether or not the value is closest to the scheduled visit date and appears in the corresponding visit-based summary.

Visit windows are described in Table 2.

Study Visit (Target Day)	Nominal Target Day	Study Visit Window (Days)		
		Lower	Upper	
Pre Screening Phase and Screening				
Phase ¹				
Visit 2 (Sereening)				
Open Label Phase			1^{1}	
OLP-Day 1	1	1	1	
OLP-Day 2 ²	2	2	2	
OLP-Day 3 ³	3	3	3	
End of OLP (24 hours or 48	2 or 3			
hours) ⁴				
End of Study Visit (OLP-Day 9) ⁵	9	4	16	
Randomized Treatment Phase				
Randomization (RTP-Day 1)	1	1	1	
Visit 6 (RTP-Day 2)	2	2	2	
Visit 7 (RTP-Day 5)	5	3	6	
Visit 8 (RTP-Day 8)	8	7	9	
Visit 9 (RTP-Day 12)	12	10	13	
Visit 10 (RTP-Day 15)	15	14	17	
Visit 11 (RTP-Day 19)	19	18	20	
Visit 12 (RTP-Day 22)	22	21	24	
Visit 13 (RTP-Day 26)	26	25	27	
Visit 14 (RTP-Day 29)	29	28	31	
End of Study Visit (RTP-Day 35) ⁶	35	32	43	

Table 2 Time windows for allocation of data to visits for statistical analysis

1. The screening phase lasts up to the date and time when the open label initial phase is initiated, i.e. date and time of the first dose.

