
2. Potassium is measured predose and 1 hour post dose. The predose measure is considered as the 24-hour measurement for all analyses. Patients who achieve normokalemia at 24 hours will proceed to the Randomization (RTP-Day 1) visit.

3. Potassium is measured predose and this measure is considered as the 48-hour measurement for all analyses.

4. End of OLP (24 hours or 48 hours) the latest treatment day of open label initial phase only for patients who complete 24 hours or 48 hours OLP treatment.

5. End of Study Visit (OLP-Day 9) in open label initial phase only for patients NOT entering the 28-day randomized treatment study phase and occurs 7±1 day after the last administration of IP.

6. End of Study Visit (RTP-Day 35) occurs 7±1 day after last planned administration of IP in RTP.

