The number of normokalemic days will be analyzed using a linear regression model with the same baseline covariates as for the primary efficacy endpoint, with the exception of visit and the visit-by-treatment interaction (see Section 4.2.1.4). The results will be presented per treatment arm. The p-value (two-sided) will be provided to compare the LSMEAN of the normokalemic days between each active treatment versus placebo.

Time to hyperkalemia

The time to hyperkalemia (days) will be summarized using Kaplan-Meier life table curves and associated 95% CI points will be provided at Days 2, 5, 8, 12, 15, 19, 22 and 29 during the RTP. Kaplan-Meier curves of the time to hyperkalemia (days) will be displayed for each treatment group.

A Cox proportional hazards model (SAS PROC PHREG) will be used with the same baseline covariates as for the primary efficacy endpoint analysis, with the exception of visit and the visit-by-treatment interaction (see Section 4.2.1.4). The hazard ratio between each active treatment versus placebo will be reported along with a 95% confidence interval and a p-value.

Mean changes in S-Aldo and P-Renin levels

Descriptive statistics will be presented for nominal values, change and percent change from baseline in S-Aldo and P-Renin levels during the RTP at Randomization (Day 1), Day 15, Day 29, and EOS for each.

This endpoint will also be analyzed using a longitudinal mixed model (SAS PROC MIXED) respectively for S-Aldo and P-Renin levels. The model will include all S-Aldo and P-Renin data values collected at the scheduled visits on Days 15 and 29 as response variables, and RTP baseline values for S-Aldo and P-Renin (respectively), baseline OLP eGFR, age (<55, 55-64, >64 years) and baseline binary indicators for RAAS inhibitors, chronic kidney disease, heart failure and diabetes mellitus as covariates.

The p-value from LSMEAN (two-sided) will be provided to compare the overall mean difference in S-Aldo and P-Renin values between each active treatment (ZS 10g and ZS 5g) and placebo. The estimated mean difference in S-Aldo and P-Renin values between each of the active treatment groups (ZS 10g and ZS 5 g) relative to the placebo treatment group will be provided along with accompanying 95% confidence intervals.

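### The SAP does not settle whether time to hyperkalaemia stops at Day 29 or runs on to the off-drug Day 35 visit

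*SAP*

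**What the plan says.** SAP 4.2.3.1 defines the endpoint as "The time to the first instance of hyperkalemia" (S-K of 5.1 mmol/L or more) and attaches no day range. The item just before it does carry one: "The number of days subjects remain normokalemic during the RTP (Day 8 to Day 29". SAP 4.2.3.2 counts time from randomisation and states that patients without an event "will be censored at the time of the last S-K measure available for the RTP". The follow-up period therefore depends on where the RTP ends.

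Text that places EOS inside the RTP:
- SAP Table 2 (3.3.3) lists "End of Study Visit (RTP-Day 35") among the rows for the randomised phase, with window Days 32-43. Its footnote says this visit "occurs 7±1 day after last planned administration of IP in RTP".
- SAP 4.2.3.3 names EOS among the RTP time points for the aldosterone and renin descriptives.
- Protocol 4.4 schedules follow-up at "Day 35 for the 28-day randomized treatment study phase", and Protocol 5.2.2 counts the Day 35 examination as part of that phase.

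Text that ends the RTP at Day 29:
- The SAP Table 3 footnotes describe the RTP as lasting 28 days and equate its end with the planned final dosing day, Day 29.
- The Kaplan-Meier read-outs in SAP 4.2.3.3 are at "Days 2, 5, 8, 12, 15, 19, 22 and 29 during the RTP".
- The Protocol synopsis and 1.4 name EOS separately from the 28-day phase.
- Protocol Table 6 limits tests 8 and 9 to hyperkalaemia in the 28-day phase.

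Potassium is measured at EOS. A footnote to Protocol Table 2 reads "Potassium will be measured fasting prior to the 1st daily dose as part of the clinical chemistry panel on Day 1, 15, 29, 35".

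**The concern.** The Day 29 and Day 35 values answer different questions. Up to Day 29 the comparison is ZS against placebo. Dosing is planned through Day 28, so Day 35 falls 35 - 28 = 7 days after the last planned dose, and the ZS arms are then off drug too.

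The design expects potassium to rise at that point. Protocol 1.2 gives recurrence after withdrawal of ZS as something the study should demonstrate, and Protocol 1.3.1 reports that potassium returned close to baseline when ZS was stopped in the long-term extension. Placebo patients still event-free at Day 29 have stayed so without drug. Event-free ZS patients include some who were held down by it.

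If EOS values count, the hazard ratio mixes maintenance on drug with planned withdrawal. The treatment-policy strategy in SAP 4.2 does not remove those values. Protocol 7.7 also allows other treatment for hyperkalaemia between the last dose and EOS, which could alter Day 35 values further.

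**Working it through.** **The plan's own figure.** No power, hazard ratio or event count is stated for this endpoint. The stated power (Protocol 8.2) is for the primary endpoint: above 90% for a difference of 0.30, SD 0.50, 100 against 50 patients, two-sided 5%.
- Standard error = 0.50 x sqrt(1/50 + 1/100) = 0.0866.
- 0.30 / 0.0866 = 3.464, and power = Phi(3.464 - 1.960) = 93.4% (93.1% with the noncentral t, 148 df).

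The stated figure is reproduced, and this point does not touch it.

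**When Day 35 matters.** All rates below are assumptions. With constant hazards, cumulative incidences to Day 29 imply a hazard ratio of ln(1 - ZS) / ln(1 - placebo):
- A: 75% placebo, 50% ZS: ln 0.50 / ln 0.25 = 0.50.
- B: 75%, 40%: ln 0.60 / ln 0.25 = 0.37.
- C: 60%, 40%: ln 0.60 / ln 0.40 = 0.56.

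The same formula, applied to event-free patients who become hyperkalaemic at Day 35, gives the ratio in that last interval. With 20% conversion on placebo (A and B):
- 10% on ZS: ln 0.90 / ln 0.80 = 0.47
- 20% on ZS: 1.00
- 50% on ZS: ln 0.50 / ln 0.80 = 3.11

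The overall ratio is pulled up whenever the last-interval ratio exceeds the ratio to Day 29. ZS rebound above placebo conversion is therefore enough, but not strictly necessary.

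**Size.** Simulated unadjusted Cox models with Efron ties, 50 placebo against 100 ZS, events at scheduled visits, 300 runs per cell. Placebo conversion at Day 35 is 20% in A and B and 15% in C. Each cell shows the hazard ratio, then power, with the Day 29 cut-off -> with Day 35 included.

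| ZS rebound | A | B | C |
|---|---|---|---|
| 10% | 0.50 -> 0.50; 87% -> 90% | 0.38 -> 0.38; 99% -> 100% | 0.56 -> 0.56; 66% -> 67% |
| 20% | 0.49 -> 0.54; 89% -> 87% | 0.37 -> 0.41; 99% -> 98% | 0.56 -> 0.65; 63% -> 50% |
| 30% | 0.50 -> 0.59; 87% -> 76% | 0.37 -> 0.47; 99% -> 95% | 0.55 -> 0.71; 65% -> 36% |
| 50% | 0.50 -> 0.66; 90% -> 56% | 0.37 -> 0.54; 100% -> 82% | 0.55 -> 0.88; 70% -> 12% |
| 70% | 0.50 -> 0.79; 92% -> 25% | 0.36 -> 0.68; 99% -> 51% | 0.56 -> 1.11; 65% -> 3% |

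Monte Carlo error on a power near 50% is sqrt(0.5 x 0.5 / 300) = 2.9 points.

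Hand check of A at 50%: 100 x 0.50 x 0.50 + 50 x 0.25 x 0.20 = 25 + 2.5 = 27.5 added events. The simulation gave 88 rising to 115.

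**A second model** simulated S-K itself (between-patient SD 0.40-0.45, within-patient SD 0.30, ZS mean back at the placebo mean by Day 35, 200 trials per scenario). It gave smaller shifts in the same direction:
- hazard ratio 0.64 to 0.68, power 65% to 54%
- hazard ratio 0.53 to 0.58, power 90% to 78%
- hazard ratio 0.47 to 0.53, power 94% to 89%

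**The case against.** The strongest reply is that the RTP already ends at Day 29. Table 3 governs tests 8 and 9, and its footnotes give 28 days and a Day 29 end. The Protocol calls EOS follow-up. SAP 4.2.1.4 describes S-K through Visit 14 and then adds EOS as a further visit. Table 2 only assigns measurements to visits: it also puts the Day 9 EOS under the open-label heading, although that phase lasts 24 or 48 hours. On this view the Day 35 row is a day-count label.

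Much of this stands. A reader might infer from Table 2 that the SAP requires Day 35 values to be counted. The documents do not support that; they support two readings.

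The reply does not close the gap, however:
- The footnote that makes Days 8-29 the period of interest cannot be the rule here. Taken literally it would drop events before Day 8, yet Kaplan-Meier points are planned at Days 2 and 5.
- The Kaplan-Meier list also omits the scheduled Day 26 visit, so it is a reporting list and not a definition of follow-up.
- Elsewhere in 4.2.3.3 the SAP limits its models by day when it means to: Days 15 and 29 for aldosterone and renin, Days 8-29 for normokalaemia. The Cox model has no such limit.

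A reader might also infer that a large loss of power is to be expected. That is not supported either. Protocol 1.3.1 gives no potassium figure at 7 days off drug, and the shift may be negligible.

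**Conclusion.** The SAP contradicts itself on the end of follow-up for a confirmatory endpoint. On one literal reading, EOS values about a week off drug could count as events in tests 8 and 9.

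The consequence depends on rates that the documents do not give. It is negligible at about 10% rebound on ZS, given 15-20% conversion on placebo; with lower placebo conversion the same 10% would matter more. It is large at 50% or more: power falls from 90% to 56% in A and from 70% to 12% in C. The simulations are unadjusted and take no account of other treatment given before EOS.

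The reach is limited. With appreciable rebound the bias runs against ZS, and including EOS does not inflate type I error. The primary endpoint and Kaplan-Meier estimates to Day 29 are untouched, and no later test depends on tests 8 and 9. The rule should still be settled before unblinding, because it decides what the hazard ratio measures.

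**What to change.** In SAP 4.2.3.2 state that:
- events count from randomisation through the Day 29 visit (analysis window to Day 31);
- event-free patients are censored at their last S-K in that period;
- S-K values after that window, including the Day 35 EOS, are excluded;
- for patients who stop early the cut-off is by study day, so S-K values within the window are kept under the treatment-policy strategy, whatever the visit label.

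The last item is needed because Protocol 4.4 sets EOS at 7±1 days after the last dose for patients withdrawn from the study. A last dose on Day 10, for example, puts EOS near Day 17. Excluding every value labelled EOS would discard data from inside the window.

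Align SAP Table 2 with the Table 3 footnotes so that the Day 35 row reads as follow-up, and make clear that the footnote on Days 8-29 does not remove earlier events from this endpoint. The cost is a few sentences, with no new data and no change to sample size.
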